#### **6.1.2 Safety Measures**

Safety measures will be applied as described below to minimize risks associated with drug-assisted psychotherapy sessions.

Participants will rate their current degree of subjective distress with a single-item, self-report scale, the SUD scale, repeatedly during the MDMA session, with the degree of distress marked along seven points. Subjective psychological distress will be measured periodically throughout each experimental session.

Cardiovascular effects will be assessed via blood pressure and pulse measurement. Blood pressure, heart rate (as pulse) and temperature will be measured periodically during each experimental session. Blood pressure and pulse will be measured at the outset of the experimental session, once every 15 minutes for the first four hours of the MDMA-assisted session and every 30 minutes for another two hours. Participants with controlled hypertension will have blood pressure and pulse assessed every 15 minutes for the first five hours and every thirty minutes for the next three hours. More frequent measurements will be taken as per the judgment of the Clinical Investigator. Blood pressure and pulse will be assessed via an automatically inflating cuff. Body temperature will be assessed via tympanic thermometer every 60-90 minutes. For subjects with a diagnosis of pre-existing controlled hypertension, the results of blood pressure and pulse measurements will be viewed by the investigators as the measurements occur. For subjects without a diagnosis of controlled hypertension, after viewing baseline values at the beginning of the session, the investigators will only view the blood pressure or pulse values in the case of a medical indication in order to improve the effectiveness of condition blinding. The night attendant will print out the blood pressure and pulse results after the session, make a back-up copy, and will seal both copies together in an envelope and write their initials over the seal. This envelope will be part of the source record and will be kept sealed until after unblinding occurs for that subject. In the event of any medical indication, such as signs or symptoms that could be related to either hypertension or hypotension, the investigators have the option to print out the results during the session.

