Blood pressure and pulse will be measured at the outset of the experimental session, once every 15 minutes for the first 4 hours of the MDMA-assisted session and every 30 minutes for another 2 hours. More frequent measures will be taken as described in section 6.1.2 if the established thresholds are exceeded, or if the subject has a diagnosis of hypertension. For subjects without a diagnosis of controlled hypertension, after viewing baseline values at the beginning of the session, the investigators will only view the blood pressure or pulse values in the case of a medical indication in order to improve the effectiveness of condition blinding. More frequent measures will be taken if the participant exhibits symptoms that could be related to hypertension, hypotension tachycardia or bradycarida. In the event of any medical indication, such as signs or symptoms that could be related to either hypertension or hypotension, the investigators have the option to print out the results during the session.

Participant body temperature will be measured via tympanic thermometer every 60-90 minutes. Participants will complete the SUD every 90 minutes, until the session is over, allowing a window of plus/minus 30 minutes to fit into the psychotherapy process where a natural break occurs. If necessary, the investigators can make a greater number of SUD measurements as their clinical judgment dictates. The investigators will record any spontaneously reported reactions during the session. If subjects who have pre-existing tinnitus or chronic pain mention any changes, the visual analog scale will be used to collect the changes in symptoms.

A supplemental dose half the size of the initial dose may be administered 1.5 to 2.5 hours after the initial dose upon mutual agreement between the investigators and the participant.

Approximately six hours after drug administration, the investigators will administer the C-SSRS.

If there is a support-individual who has previously been asked and has agreed to be present during part or all of the MDMA session, that person may arrive during the session at whatever time has been agreed upon, but will wait in the waiting room until brought back to the session room by one of the therapists.

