#### 7.4.1 Cardiovascular Effects

The full dose of 125 mg, followed by a supplemental dose of 62.5 mg after 1.5 to 2.5 hours, is expected to produce significant but transient, self-limited increases in blood pressure and heart rate. Participants enrolled in controlled trials with MDMA (approximately 5% per trial) have had elevations in blood pressure of above 140/90 mmHg or higher, but none of these individuals needed clinical intervention and blood pressure returned to normal as drug effects waned [68, 75]. Table 2 shows the degree of increase in vital-sign measurements in the investigators' recently completed clinical trial. No subjects in other clinical trials using MDMA have required any clinical interventions for elevated blood pressure, pulse or temperature, and all values returned to normal spontaneously.

The degree of additional blood pressure and pulse elevation after a second dose of MDMA that is half the original dose and given 1.5 to 2.5 hours after the first dose is minimal. Preliminary data gathered by [name], the Clinical Investigator who recently conducted a study of MDMA-assisted psychotherapy in 21 participants PTSD, demonstrates that elevation in blood pressure and heart rate after the supplemental dose does not exceed elevations seen after the initial dose.

Table 2. Physiologic Data: Mean Increases in Vitals over Baseline and Range of Values per Experimental Session

	MDMA	Placebo
	Mean increase (St. Dev.)	Mean increase (St. Dev.)
	[Range of values]	[Range of values]
Systolic blood		
pressure, mmHg	28.21 (14.11)	13.38 (10.40)
	[96-179]	[83-157]
Diastolic blood		
proggura mmUa	15.38 (6.85)	10.94 (6.93)
pressure, mmHg	[56-113]	[60-102]
Heart rate,		
beats/minute	28.13 (11.87)	16.69 (12.35)
	[60-141]	[68-107]
Temperature, °C	0.72 (0.52)	0.42 (0.32)
	[36.6-37.83]	[36.39-37.76]

Group comparisons of vital signs were tested for change pre-session (15 minutes prior) to highest recorded and pre-session to post-session (6 hours post) using t-tests. There was a significantly greater increase in all physiologic measures from pre-session to highest recorded value during experimental sessions for the MDMA group than for the placebo group (p < .05). There were no significant differences when comparing changes from pre-session to post session (p > .05). All values returned to pre-session norms by six hours after session completion.

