an exploratory intent to treat analysis to examine results without bias towards subjects more likely to complete the study per protocol.

Descriptive statistics will be computed for vital signs and subjective distress during each experimental or open-label session. The sponsor will informally or formally compare peak blood pressure, heart rate and body temperature for participants after sessions after low, medium or full dose MDMA. Frequency tables will be produced on prevalence of spontaneously reported reactions and AEs.

The sponsor will collect Changes in Tinnitus and/or Pain visual analog scale scores from any subject reporting tinnitus or chronic pain during each point of administration, including baseline, experimental and integrative sessions, the primary endpoint, and two-month follow-up. The sponsor will plot and examine all Changes in Tinnitus and/or Pain visual analog scale scores across all three groups and within the dose groups for trends. Formal analysis of Changes in Tinnitus and/or Pain visual analog scale scores will only occur if three or more subjects complete Changes in Tinnitus and/or Pain visual analog scale at baseline and primary endpoint. Likewise, formal between-groups analyses will not be performed if all primary endpoint scores are from subjects assigned to the same condition. The sponsor will perform an independent t-test on the difference between baseline and primary endpoint Changes in Tinnitus and/or Pain visual analog scale scores in the full dose and comparator dose conditions, with p. set at 0.05. If the only scores available are for subjects in a single condition, then a paired t-test will be performed comparing baseline and primary endpoint Changes in Tinnitus and/or Pain visual analog scale scores, with p. set at 0.05.

Descriptive statistics will be computed for SOCQ scores completed after each MDMA-assisted psychotherapy session, and SOCQ scores will be compared across each of the three MDMA dose conditions and after full dose given during Stage 2. The data will be explored for effects of condition on responses to the SOCQ.

Descriptive statistics will be calculated for subject's perceptions of experimental sessions. Mean, standard deviation and range of individual responses will be examined. Perceptions of experimental sessions will be examined during Stage 1 and Stage 2, before and after participant have undergone a third experimental session and will be compared within subjects.

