### 3.3 Safety Objectives

- Suicidality will be assessed with the Columbia Suicide Severity Rating Scale (C-SSRS) before, during and after experimental sessions and on selected days of telephone or face-to-face contact, with comparisons made between subjects in each condition.
- Subjective Units of Distress (SUD) and vital signs (blood pressure, heart rate and temperature) will be measured during each experimental session, and comparisons will be made for vital signs between conditions.
- Collect changes to pre-existing tinnitus and/or chronic pain symptoms using a visual analog scale, specifically in subjects with a medical history of tinnitus and/or chronic pain.
- Serious adverse events, adverse events and spontaneously reported reactions will be collected during the study according to Section 8.3

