### Subjective Units of Distress (SUD)

Descriptive statistics for SUD scores will be calculated by treatment group and time period with counts and percentages.

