### Vital signs

Vital signs (heart rate, body temperature, systolic and diastolic blood pressure) will be summarized using descriptive statistics at baseline and at each post-baseline time point. For experimental sessions, mean peak heart rate, blood pressure, and body temperature will be analyzed by condition with ANOVA, with t-tests for pairwise comparisons. Occurrences of systolic and diastolic blood pressure, heart rate, and body temperature readings above the pre-determined cutoff will be displayed with numbers and percentages by timepoint. A within-subjects t-tests for pre- and post-drug endpoints will be conducted for each session for heart rate, blood pressure, and body temperature.

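### The planned table of vital-sign readings above the cutoff is specified by timepoint only, with no count of subjects who ever exceed it and no split by dose

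*SAP*

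**What the plan says.** The Vital signs paragraph of SAP 8.9.4 plans four things: descriptive statistics at baseline and at each later time point; a dose comparison of peaks, in which "mean peak heart rate, blood pressure, and body temperature will be analyzed by condition with ANOVA", with pairwise t-tests; the exceedance display, in which "readings above the pre-determined cutoff will be displayed with numbers and percentages by timepoint"; and within-subject pre/post t-tests for each session. The exceedance sentence names no dose condition, no subject-level count, no denominator and no cutoff value.

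The SAP's safety objective (3.3) is that "comparisons will be made for vital signs between conditions". Protocol 12.0 says that the sponsor will "informally or formally compare peak blood pressure, heart rate and body temperature for participants", across the dose levels.

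Other safety displays in 8.9.4 are more explicit. Adverse events are counted once per subject per preferred term and shown by treatment group. C-SSRS responses are tabulated by treatment group and time period. For distress ratings, "Descriptive statistics for SUD scores will be calculated by treatment group and time period with counts and percentages".

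Protocol 6.1.2 sets two schedules for blood pressure and pulse. Most subjects are read every 15 minutes for four hours, then every 30 minutes for two more. By contrast, "Participants with controlled hypertension will have blood pressure and pulse assessed every 15 minutes for the first five hours", then every 30 minutes for three more. Temperature has one schedule, every 60 to 90 minutes, for all. Extra readings are allowed at the investigator's judgment.

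**The concern.** Protocol 7.4.1 says that the full dose with its supplement "is expected to produce significant but transient, self-limited increases in blood pressure and heart rate". For a short-lived rise, two questions matter: how many subjects crossed the cutoff at any time, and whether that number goes up with dose. A table of readings by timepoint answers neither. Subjects need not cross at the same time, and an optional supplemental dose 1.5 to 2.5 hours after the first may spread the times further.

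The figure also has a use outside this trial. Protocol 7.4.1 describes earlier trials by the percentage of participants whose blood pressure rose above a level, so a per-subject percentage is the natural comparator. This is also the first study in the programme to admit controlled hypertension.

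If the table stays as worded, the subject-level figure by dose would have to come from the data listings. SAP 8.0 keeps data not analysed under the plan out of tables and graphs, and any later count would be labelled post hoc.

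**Working it through.** The plan gives no cutoff value for this display and no expected exceedance rate, so there is no figure of its own to reproduce. Three checks can be made from the documents alone.

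**1. Do row percentages determine the share of subjects ever above the cutoff?** Take the full-dose group, n = 12, and the 20 post-start readings derived in check 3. Suppose that exactly one subject is above the cutoff in each row, so every row shows 1/12 = 8.3%.
- Lower bound: the same subject every time, 1/12 = 8.3%.
- Upper bound: a different subject each time until all are used, min(20, 12)/12 = 12/12 = 100%.

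The table is identical in both cases.

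**2. Does a count without a dose split show the gradient?** With 12, 6 and 6 subjects at full, medium and low dose, suppose that 5 of 24 are above the cutoff (20.8%).

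| Split (full, medium, low) | Full | Medium | Low |
|---|---|---|---|
| 5/12, 0/6, 0/6 | 41.7% | 0% | 0% |
| 3/12, 1/6, 1/6 | 25.0% | 16.7% | 16.7% |
| 1/12, 2/6, 2/6 | 8.3% | 33.3% | 33.3% |

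All three splits give the same 5/24, although the gradient points in opposite directions in the first and last.

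**3. Do the timepoints share a denominator?** This check assumes that a timepoint is a scheduled reading, and uses the schedules in Protocol 6.1.2 for blood pressure and pulse.
- Without controlled hypertension: 4 h × 4 per hour + 2 h × 2 per hour = 16 + 4 = 20 readings after the start (21 with the reading at the outset).
- With controlled hypertension: 5 × 4 + 3 × 2 = 20 + 6 = 26 (27 with the outset).
- Times only on the second schedule: 4:15, 4:45, 6:30, 7:00, 7:30 and 8:00 h, which is 26 − 20 = 6 rows. All four scheduled rows after 6 h are among them.

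Those six rows would hold only subjects with controlled hypertension, if any enrol. The SAP introduction treats their enrolment as a possibility, so the rows may be empty. None of this applies to temperature, and unscheduled readings from other subjects could fall at or near those times.

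**Cutoff.** SAP 8.9.4 calls it pre-determined without giving it. Protocol 6.2.3 says "More frequent measures will be taken as described in section 6.1.2 if the established thresholds are exceeded", but 6.1.2 lists no thresholds. The temperature rises over baseline in Appendix A (1 °C and 1.5 °C) and the 140/90 level mentioned elsewhere in the protocol are not linked to this display.

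**The case against.** The strongest reply is that the safety objective is already met. Peak values are compared by condition, and a peak is a per-subject maximum, so differences in the time of peak are dealt with there. This stands: a dose gradient in vital signs is analysed, and only the gradient in exceedance is missing. It does not close the gap, because a modest mean can coexist with a few subjects far above a cutoff, and the SAP itself treats exceedance as a separate display.

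Second, a reader might infer that the SAP merges the three doses. It does not say so; it is silent. The by-group rule opening SAP 8.9 could be read as covering the table, although it is worded for primary, secondary and exploratory endpoints.

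Third, timepoint is undefined. SAP 8.9.1 and 8.9.2.1 use the word for a visit. If it means a session here, the argument about unequal rows falls. The paragraph's opening reference to each post-baseline time point makes a within-session reading plausible but does not settle it.

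Fourth, a reader might infer that row percentages greatly understate incidence. The documents do not support a size. An illustration used the earlier-trial systolic increase under MDMA in Protocol 7.4.1 (28.21, SD 14.11), with an assumed resting value of 120 (SD 10), an assumed single-peaked response curve with its peak between 1 and 3.5 h, and example cutoffs. Full-dose ever-above was 24.7% against 20.9% in the highest row at 160, and 68.1% against 65.1% at 140. Like for like, that is a gap of 3 to 4 points. Much larger contrasts appear only if doses are pooled or rows far from the peak are averaged in.

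Finally, this is a 24-subject pilot and post hoc analyses are allowed. That limits the weight of the point, but the change is also very small.

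**Conclusion.** The concern holds in a limited form. As specified, the exceedance display gives no count of subjects ever above the cutoff and no dose split. Neither can be derived from it, as the 8.3% to 100% range and the three splits of 5/24 show. This sits awkwardly with a between-condition safety objective and with adverse-event, C-SSRS and distress displays that do name the treatment group.

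Three stronger statements are not supported: that no dose comparison of vital signs is planned, that the doses are pooled, and that late rows necessarily contain only hypertensive subjects. The last holds only for scheduled blood pressure and pulse rows at 4:15, 4:45 and after 6 h, only if timepoints are scheduled readings, and only if such subjects enrol.

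The size of any understatement in this trial is unknown. It depends on a cutoff that neither document states for this display and on response curves that would have to be assumed; the simulated figures should not be quoted as its size. This is a worthwhile reporting improvement and does not affect the efficacy analysis.

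**What to change.** In SAP 8.9.4, Vital signs:

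- Add a table giving, per vital sign and experimental session, the number and percent of subjects with at least one reading above the cutoff, by dose condition. State the denominator, for example Safety Population subjects with at least one post-dose reading in that session.
- Show it in two parts: (a) scheduled readings to 6 h that are common to all subjects, so without 4:15 and 4:45 for blood pressure and pulse, as the like-for-like dose comparison; (b) all readings, with unscheduled readings and the extended readings of subjects with controlled hypertension identified separately. Part (b) is needed because part (a) alone would drop readings prompted by symptoms.
- Show the open-label sessions (Stage 1 session 3 and Stage 2) separately from the blinded ones.
- Keep the by-timepoint table as supportive, split by dose, and define timepoint.
- Reconcile the SAP's cutoff with the thresholds that Protocol 6.2.3 attributes to 6.1.2, where none are listed. No value is proposed here, but the table cannot be run until this is done.

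The cost is a few lines of SAP text and one descriptive table, from readings that the SAP already plans to summarise. Nothing changes in visits or patient management. The groups are small: with 12, 6 and 6 subjects, one subject is 8.3%, 16.7% and 16.7%, so counts should be shown beside every percentage.

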## **8.10 Timing of Analyses**

The primary efficacy analysis will be conducted after all subjects complete Stage 2, but before all long-term follow-up data has been collected. Subsequent analyses on this data set will not be conducted after initial analyses are performed, unless for further exploratory post-hoc analyses. Changes to protocol will not occur after primary analysis. The final analysis of secondary endpoints will include only data not analyzed in the primary efficacy analysis, i.e. data will not be analyzed twice.

